### **Causality Assessment**

The following decision choice will be used by the investigator to describe the causality assessment between the reported event and the investigational medicinal product.

- Unrelated: No relationship between the AE and the administration of investigational product; related to other etiologies such as concomitant medications or subject's clinical state.
- Unlikely: Event or laboratory test abnormality with a time to study medication intake that makes a relationship improbable (but not impossible). Disease or other drugs provide plausible explanations.
- Possible: Event or laboratory test abnormality with reasonable time relationship to study medication intake which could also be explained by disease or other drugs. Information on drug withdrawal may be lacking or unclear.
- Probable: Event or laboratory test abnormality with reasonable time relationship to study medication intake. Event unlikely to be attributed to disease or other drugs. Response to withdrawal is clinically reasonable and rechallenge not required.
- Certain: Event or laboratory test abnormality, with plausible time relationship to study medication intake that cannot be explained by disease or other drugs. Response to withdrawal is plausible (pharmacologically, pathologically). Event definitive pharmacologically or phenomenologically (i.e. an objective and specific medical disorder or a recognized pharmacological phenomenon). Rechallenge satisfactory, if necessary.

### **Action Taken Regarding Investigational Product**

The action taken must be described by choosing among:

- Dose not changed: No action is taken regarding the study medication.
- Study medication permanently withdrawn: Subject is permanently withdrawn from the study.
- Study medication temporarily withdrawn: Study drug is temporarily withdrawn.
- Not applicable: Other situations (e.g., AE started after the last study medication administration)

### **Outcome**

Each AE must be rated by choosing among:

- Recovered/resolved.
- Recovered/resolved with sequelae.
- Not recovered/not resolved.
- Fatal.
- Recovering/resolving.
- Unknown.

#### **8.7.1.4.1.2 Recording Adverse Events**

AEs will be recorded from the signature of ICF until the final Follow-up visit. If an AE is ongoing at that time, it will be followed up until resolution or until stabilization, according to the investigator's medical judgement.

It is the responsibility of the investigator to collect all AEs (both serious and nonserious) derived by spontaneous, unsolicited reports of subjects, by observation, and by routine open questioning (such as "How do you feel?").

Any adverse or unusual event occurring during or after the clinical study (until the Follow-up visit or the moment of rollover to the Follow-up study GLPG0634-CL-205), whether observed by the investigator or investigational staff, or spontaneously reported by the subjects will be recorded in the eCRF.

#### **8.7.1.4.1.3 Managing Serious Adverse Events**

Subjects experiencing an SAE or an emergency situation will be examined by a physician as soon as possible. The physician in attendance will do whatever is medically needed for the safety and well-being of the subject. The subject will remain under observation as long as medically indicated. Appropriate laboratory studies will be conducted until all parameters return to normal or are otherwise explained or stable. The subject will be followed until the SAE resolves or until the subject is medically stabilized.

#### **8.7.1.4.1.4 Reporting Serious Adverse Events to [REDACTED]**

All SAEs, whether or not deemed study medication-related, must be recorded in the eCRF and SAE form and reported by the investigator to [REDACTED] ([REDACTED]), [REDACTED] (Belgium) within 24 hours by facsimile. Other means of transmission can be decided where facsimile is not possible. The SAE should include a clearly written narrative describing signs, symptoms, and treatment of the event, diagnostic procedures, as well as any relevant laboratory data and any sequelae.

Follow-up and outcomes should be reported for all subjects that experience an SAE. It is critical that the information provided on the [REDACTED] SAE form matches the information recorded on the eCRF for the same event. In addition, the same information is to be recorded in the source documents.

Copies of additional laboratory tests, consultation reports, post-mortem reports, hospital case reports, autopsy reports, and other documents should be sent when requested and applicable. Follow-up reports relative to the subject's subsequent course must be submitted to [REDACTED] until the event has subsided or, in the case of permanent impairment, until the condition stabilizes.

The contact persons are:

Name and Title	Telephone no.	Fax no.	E-mail
[REDACTED]	[REDACTED]	[REDACTED]	[REDACTED]
Medical Safety Officer*	[REDACTED]	[REDACTED]	[REDACTED]

\* The Medical Safety Officer at Galapagos is the sponsor liaison for [REDACTED] assessment of SAEs.

**8.7.1.4.1.5 Pregnancy**

All initial reports of pregnancy in a subject and pregnancies in partners of male subjects included in the study must be reported to [REDACTED] by the investigator using a pregnancy form within 24 hours of knowledge of the event. Any subject who becomes pregnant during the study must be promptly withdrawn from the study (not applicable if the subject is male). Spontaneous abortion is considered an SAE and will be reported as such.

The investigator will contact the subject at the expected time of delivery for follow-up on the pregnancy outcome. Abnormal pregnancy outcomes are considered SAEs and must be reported using the SAE form.

**8.7.1.4.1.6 Reporting Serious Adverse Events to Competent Authorities/ Ethics Committees**

[REDACTED] assumes responsibility for appropriate reporting of AEs to the regulatory authorities. [REDACTED] will also report to the investigator(s) all SAEs that are unlisted (unexpected) and associated with the use of the study medication. The investigator(s) (or [REDACTED] where required) must report these events to the appropriate IEC/IRB that approved the protocol unless otherwise required and documented by the IEC/IRB.

AE reporting, including suspected unexpected serious adverse reactions, will be carried out in accordance with applicable local regulations.

After termination of the clinical study (last subject last contact in the study), any unexpected safety issue that changes the risks benefit analysis and is likely to have an impact on the subjects who have participated in it, will be reported by the sponsor, [REDACTED] as soon as possible to the competent authority(ies) concerned together with proposed actions.

**8.7.1.4.2 Clinical Laboratory Evaluation**

The hematology, clinical chemistry, and urinalysis laboratory analyses will be performed at a central laboratory ([REDACTED]). Reference ranges will be supplied by the central laboratory and used by the investigator to assess the laboratory data for clinical significance and pathological changes.

The total amount of blood to be taken during the study will not exceed 600 mL.

The following laboratory safety tests will be performed at every visit:

### **Hematology**

Hemoglobin, hematocrit, WBC count (total and differential), RBC count, differential lymphocyte count (by flow cytometry; CD3, CD19, CD4, CD8, CD3-/CD16+, and CD56+), platelet count, activated partial thromboplastin time, and prothrombin time.

### **Clinical Chemistry**

Creatinine, blood urea nitrogen (BUN), AST, ALT, gamma glutamyltransferase (GGT), alkaline phosphatase, total bilirubin, amylase, lipase, albumin, total protein, sodium, potassium, chloride, glucose, uric acid, total cholesterol, HDL and LDL, triglycerides, calcium, phosphorus, and CRP.

Serum pregnancy test for females of childbearing potential at Screening and Week 24 only or EDV only.

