## **6.2 Background on GLPG0634**

Janus kinases are intracellular cytoplasmic tyrosine kinases (TYKs) that transduce cytokine signaling from membrane receptors to the nucleus of cells. JAK inhibitors block the signaling of various cytokines, growth factors and hormones, including the pro-inflammatory cytokine interleukin (IL)-6. Four different types of JAKs are known which (co-)interact with different sets of membrane receptors: JAK1, JAK2, JAK3 and TYK2. Inhibition of JAKs is a promising therapeutic option for a range of inflammatory conditions including RA and Crohn's disease (CD).

GLPG0634 is a potent and selective inhibitor of JAK1. The compound is currently in phase II development for RA and CD and has shown good preliminary efficacy in RA patients. No typical JAK2 side effects such as anemia were observed in clinical studies. The anticipated therapeutic daily dose range is 50 to 200 mg.

GLPG0634 is metabolized to form one major active metabolite, G254445. Though the potency of this metabolite is lower than the parent molecule, the overall exposure and peak plasma concentration in humans is higher. As a consequence, dedicated pharmacology and toxicology studies have been performed with G254445. Results from pharmacodynamics (PD) testing in healthy volunteers suggest that the clinical activity of GLPG0634 could result from the combination of the parent molecule and the metabolite.

More information on the study drug along with references to support the cited data are presented in the Investigator's Brochure (IB). A summary is provided hereafter.

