## **8.7.1 Efficacy, Pharmacokinetics, Pharmacodynamics and Safety Measurements Assessed and Flow Chart**

### **8.7.1.1 Efficacy Assessments**

#### **8.7.1.1.1 Evaluation of Disease Activity**

Efficacy assessments will be carried out at Screening (joint counts and Patient's Global Assessment of Disease Activity only); Baseline (Day -1); Weeks 1, 2, 4, 8, 12, 16, 20, and 24; and the EDV (if applicable).

Each of 68 joints will be evaluated for tenderness, and each of 66 joints will be evaluated for swelling (Appendix 13.2).

A joint assessor with adequate training and experience in performing joint assessments will be designated at each study site to perform all joint assessments. The joint assessor should preferably be a rheumatologist; however, if a rheumatologist is not available, it should be a health care worker with at least one year's experience in performing joint assessments. The assessor should remain the same throughout the study per subject, as much as possible. It is required that the designated joint assessor identify an appropriate back-up assessor to provide coverage if the designated joint assessor is absent.

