#### **8.8.1.3 Efficacy Variables**

##### **Definition of Primary Efficacy Endpoint – ACR20 at Week 12**

The primary endpoint is the percentage of subjects achieving an ACR20 response at Week 12. Other time points will be regarded as secondary endpoints.

The ACR response is a measurement of improvement in multiple disease assessment criteria. The ACR20 response is defined as:

≥20% improvement from Baseline in SJC66 (66 joints) and TJC68 (68 joints)

AND

≥20% improvement from Baseline in at least 3 of the following 5 assessments

CONFIDENTIAL

- Pain (VAS) in cm (from HAQ-DI).
- Patient's Global Assessment of Disease Activity (VAS) in cm.
- Physician's Global Assessment of Disease Activity (VAS) in cm.
- Patient's Assessment of Physical Function as measured by HAQ-DI.
- CRP in mg/dL or mg/L.

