8.8. ACR COMPONENT: SERUM CRP

8.8.1. Parameters

Serum CRP (mg/L) will be analyzed as raw values, change from baseline and percent change from baseline.

Note that if for a specific visit both the regular CRP as well as the high-sensitive CRP are available, the high-sensitive CRP will be used in the analysis tables and figures. The regular CRP will then only be listed.

CRP and hsCRP values will also be categorized according to the lab's normal ranges: normal (value \leq ULN) or high (value $>$ ULN), where ULN = upper limit of the normal range as provided by the central lab. Note that the same ULN (8.999) will be applied to both CRP and hsCRP.

Note that CRP and hsCRP will be excluded from the lab safety analysis.

Note that the percentage change from baseline remains missing if the baseline value itself equals zero.

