12.2. LABORATORY SAFETY**12.2.1. Laboratory Units**

The statistical analysis will only present results in Standard International (SI) units. Other units will not be presented.

Lab tests with only a very low sample size ($N < 3$ in the study total column) will not be presented in the tables, but only in the listings. Lab tests that are not part of the planned test panels according to the protocol will only be listed.

Endocrine tests will only be presented for male subjects. If any results would be available for females (not planned in the protocol), then these will be left out of the tables but still presented in the listings.

Urinalysis tests will be presented as part of the descriptive statistics and/or shift tables.

The serum CRP will not be presented in this section (is considered an efficacy parameter).

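### Post-Baseline CRP, an efficacy component, sits in the chemistry panel the investigator reviews, and nothing in the protocol masks it from the Physician's Global and joint raters, who may guess active versus placebo

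*Protocol*

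**What the plan says.** **CRP in the reviewed panel.** Protocol Section 8.7.1.4.2 introduces its lists with "The following laboratory safety tests will be performed at every visit". The Clinical Chemistry list ends with "uric acid, total cholesterol, HDL and LDL, triglycerides, calcium, phosphorus, and CRP". The same section says that central-laboratory reference ranges are "used by the investigator to assess the laboratory data for clinical significance and pathological changes". No analyte is exempted.

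**CRP as efficacy.** The ACR20 definition in Protocol Section 8.8.1.3 lists "CRP in mg/dL or mg/L" among the five non-joint items, of which three must improve. CRP also enters DAS28(CRP), SDAI and ACR/EULAR remission. SAP Section 8.8.1 states: "Note that CRP and hsCRP will be excluded from the lab safety analysis". SAP Section 12.2.1 gives the reason: "The serum CRP will not be presented in this section (is considered an efficacy parameter".

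**The raters.** Section 8.7.1.1.1 assigns joint counts to a designated, trained site assessor with a back-up. It adds "The joint assessor should preferably be a rheumatologist" and is silent on access to laboratory results. Section 8.7.1.1.3 requires the physician's rating to be independent of the subject's rating and sets no other condition.

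**Blinding.** Section 8.5.7 covers treatment assignment, and Section 8.5.2 matches the capsules. Neither mentions laboratory values.

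**Mechanism.** Section 6.2 says "JAK inhibitors block the signaling of various cytokines, growth factors and hormones, including the pro-inflammatory cytokine interleukin (IL)-6". Section 8.8.1.8 names CRP as an exposure-response endpoint.

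**The concern.** ACR20 cannot be met without a 20% improvement in both joint counts. Those counts and Physician's Global are scored by site staff. If those staff can follow a subject's CRP from Week 1 and the drug lowers CRP, the laboratory report carries information about treatment even though the capsules match. Expectation could then raise scores in subjects thought to be on active drug, in the direction that favours the drug on the primary endpoint.

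The exposure appears unnecessary. The CRP eligibility limit applies at Screening (Section 8.3.2). None of the listed laboratory withdrawal thresholds in Section 8.3.4 names CRP. The Week 12 reassignment uses SJC66 and TJC68 through IXRS. SAP Section 6.2 goes as far as blanking sparse table cells to protect the blind at the interim, so leaving individual CRP values open at sites is out of step with the rest of the plan.

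**Working it through.** **1. The plan's own figures.** Section 8.8.2 gives n = 70 per arm and alpha = 5%/3 = 1.67% per comparison. A two-sided pooled chi-square calculation gives power of 0.907 (15% vs 43%) and 0.891 (40% vs 70%) against the stated 90%. It gives 0.798 (15% vs 39%) and 0.800 (40% vs 67%) against the stated 80%. The design inputs reproduce. None of them bears on masking.

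**2. What CRP could reveal.** The documents show no CRP effect, and the step from IL-6 to CRP is an assumption. Assume a log-CRP shift of -1.0 on active (median fall 1 - e^-1 = 63%) with SD 0.93.
- Standardised difference: d = 1.0/0.93 = 1.075.
- Best single cut-off (log change -0.5): sensitivity minus false-positive rate = 2Φ(d/2) - 1 = 2(0.705) - 1 = 0.41.
- Active versus placebo: AUC = Φ(d/√2). For differences of 0.5, 1.0, 1.5 and 2.0 SD this is 0.64, 0.76, 0.86 and 0.92.
- Exact arm of four, with the doses spread around those differences: guessed correctly 31%, 37%, 43% and 49% of the time (chance 25%).

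CRP is therefore a moderate clue to active versus placebo and a poor clue to dose.

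**3. Effect on ACR20, by simulation.** Six clinical components are normal on percent improvement (assumed SD 40, common correlation 0.5), with CRP as in step 2 and drawn independently of them. Component means are set to give the ACR20 rates shown, taken from Section 8.8.2. The rater adds 10 points to Physician's Global, and 0, 5 or 10 points to each joint count, for any subject in either arm whose log-CRP change is below -0.5. Net bias is the gain in the active arm minus the gain in the placebo arm, in percentage points.

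| ACR20 placebo / active before bias | Physician's Global only | plus 5 in joints | plus 10 in joints |
|---|---|---|---|
| 15% / 15% | 0.2 | 1.3 | 2.4 |
| 40% / 40% | 0.3 | 2.0 | 3.8 |
| 15% / 43% | 0.3 | 2.6 | 4.7 |
| 40% / 70% | 0.1 | 1.5 | 2.7 |

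Example from row 1, last column: active gains 4.31 and placebo gains 1.92, so the net is 2.39.

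If instead every active subject and no placebo subject were recognised, the same rows give 0.5 to 0.7, 3.1 to 5.0 and 5.7 to 9.0.

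**4. What such a bias would do to the test.** With no true effect and a net bias b, the chance of a positive result favouring active is Φ[(b - z·SE0)/SE1]. Here z = 2.394, SE0 is the pooled and SE1 the unpooled standard error. For placebo 15% and b = 0.03: (0.03 - 2.394 × 0.0627)/0.0627 = -1.92, which gives 2.8%. For b from 0.01 to 0.04 the range is 1.3% to 3.9% (placebo 15%) and 1.2% to 2.8% (placebo 40%). The nominal value is 0.83%.

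**The case against.** **Release to sites is inferred.** The protocol says the investigator assesses laboratory data. It does not say which post-Baseline values are sent. The visit schedules and flow chart list serum CRP separately from clinical chemistry, and a laboratory manual outside these documents might already mask it. This stands as a caveat. The chemistry list nevertheless includes CRP without exception, and the protocol should state any masking.

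**The joint assessor may never see CRP.** This is a designated role and nothing says it has laboratory access. Nothing forbids access either, or bars the investigator from the role. The objection matters because, without the joint route, the effect is only tenths of a point.

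**Timing.** Samples go to a central laboratory and turnaround is not stated. A rater would probably hold earlier visits' values. Those still inform scoring at Week 12.

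**CRP may have a safety use.** The protocol calls the panel safety tests and Section 6.5 promises close infection monitoring. Section 8.3.4 also lets the investigator act on any clinically significant laboratory result. The SAP decides only where CRP is tabulated. This is a fair reason for a release route.

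**The remedy is partial and may be late.** Section 8.8.1.8 names neutrophils and LDL as possibly altered by treatment, and they would stay visible. SAP version 2.0 follows the interim lock, so masking cannot change Week 12 scores already recorded. Both are true, but neither removes the gap in the protocol as written.

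**Stronger readings a reader might infer.** One is that CRP lets raters identify the arm. With three active doses, step 2 does not support that. Another is that the apparent dose-response is biased. The documents give no CRP effect by dose, and the simulation has one active shift, so nothing here quantifies it.

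**Conclusion.** The gap is real and modest. Post-Baseline CRP is an efficacy variable in a panel that the investigator reviews, and no provision masks it or shields the raters. Raters might guess active versus placebo.

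The size of any bias is unknown. On the stated assumptions it is about 0.1 to 0.3 percentage points through Physician's Global alone. It is roughly 1 to 4 points (4.7 in the most adverse row) if the joint assessor also sees CRP and shifts joint counts by 5 to 10 points. Against the 28- to 30-point differences the study is sized on, 1 to 4 points is about 3% (1/30) to 14% (4/28). The rater biases, component SD, correlation and CRP shift are all assumed, with no source in the documents. A reader might be drawn to a figure of 6 to 9 points, but that requires perfect recognition of treatment, which CRP does not give.

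This is an inexpensive improvement to blinding. It is not evidence that the primary result would be invalid.

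**What to change.** In Protocol Sections 8.5.7 and 8.7.1.4.2, state that the central laboratory withholds all post-Baseline CRP and hsCRP values from site staff and blinded study personnel until the Week 24 database lock, with these exceptions:
- the independent interim statistician, and the data handling needed for the Week 12 interim, whose outputs use CRP (Protocol Section 8.8.1.5, SAP Section 6.2);
- the DSMB;
- release to the investigator through the Medical Monitor when needed for safety.

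If a laboratory manual already masks CRP, one cross-referencing sentence is enough.

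The cost is a change to central-laboratory reporting and a short amendment. The downsides are that the investigator no longer sees CRP routinely and that other drug-responsive analytes stay visible. Samples, assays, sample size, alpha and the SAP analyses are unchanged.

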### **Hormone tests (for male subjects only)**

Testosterone (total and free), LH, FSH, prolactin, and inhibin B.

